3.1.2.2 Rules for Dose Modification and Changes in Dose Scheduling following Dose-Limiting Toxicity

Dose modification following the DLT window will occur in accordance with the following rules:

- The safety cohort will enroll up to 6 patients.
- *If DLTs are observed in ≥33% of patients (i.e., 2 or more of 6 patients) in this initial safety cohort, a dose de-escalation cohort of 6 patients will be enrolled. The dosing schedules for this de-escalation cohort will be as follows:*
 - *Atezolizumab will be administered to patients by IV infusion at a fixed dose of 840 mg, starting on Day 22 of Cycle 1. In subsequent cycles, 840 mg of atezolizumab administered by IV infusion will be given Q2W on Days 8 and 22 of each 28-day cycle.*
 - *Hu5F9-G4 will be given as two priming doses of 1 mg/kg IV on Days 1 and 4, followed by loading doses of 10 mg/kg IV on Day 8 and 15 mg/kg on Day 11. Starting on Day 15, maintenance treatment with Hu5F9-G4 will be given by IV infusion at a dose of 15 mg/kg QW.*
 - *If a DLT is observed in ≥33% of patients (i.e., 2 or more of 6 dose de-escalation patients), the dose and schedule will be considered intolerable and the MTD will have been exceeded.*

- The dose level(s) and schedule at which *<33% of patients (i.e., 1 or fewer of 6 dose de-escalation patients) experience a DLT will be declared the optimal dose and schedule and an expansion cohort of 9 patients will be enrolled using the same dosing regimen.*
- *If DLTs are observed in <33% of patients (i.e., 1 or fewer of 6 patients) in the initial safety cohort, an expansion cohort of 15 patients will be enrolled to further test the safety and anti-tumor activity of atezolizumab in combination with Hu5F9-G4, using the same dosing regimen.*

3.1.2.3 Definition of Dose-Limiting Toxicity

A DLT is defined as any of the following adverse events that are causally related to study treatment that occur during the DLT assessment window and are considered by the investigator to be related to atezolizumab, *Hu5F9-G4*, or the combination of atezolizumab with *Hu5F9-G4* (see Section 5.3.4, Table 5, for guidance on causal attribution). For potential overlapping toxicities, investigators are encouraged to perform additional testing, such as tissue biopsy, imaging, peripheral blood smears, immunological assays, and other laboratory studies to determine the underlying etiology and appropriate attribution (whether the event is related to atezolizumab, *Hu5F9-G4*, or the combination of atezolizumab and *Hu5F9-G4*. Testing is to be determined by the investigator, according to local medical standards, and if needed, in consultation with the Medical Monitor, based on an individual patient's clinical presentations. Testing may elucidate whether the event is an immune-mediated adverse event caused by atezolizumab, including those events listed in Section 5.2.3 that should be reported to the Sponsor immediately (i.e., within 24 hours).

Any of the following adverse events that occur during Cycles 1 or 2 will be considered a DLT (if causality is determined to be yes according to Table 5) for atezolizumab alone or in combination with *Hu5F9-G4*:

- Any adverse event (regardless of NCI CTCAE v5.0 grade) that leads to dose reduction or withdrawal
- Any infusion-related toxicity Grade ≥ 3 (e.g., allergic reaction/hypersensitivity, fever, pain, bronchospasm, wheezing, or hypoxia)
- Hypocellular ($\leq 5\%$ cellularity) or aplastic bone marrow ≥ 3 without evidence of MDS, leukemia, or infectious etiology that lasts for ≥ 35 days from the first occurrence
- Grade ≥ 3 liver enzyme (ALT or AST) and Grade ≥ 3 creatinine elevations
- Grade ≥ 3 thrombocytopenia associated with clinically significant bleeding that requires transfusion of red cells and platelets
- Grade ≥ 3 non-hematologic adverse events (with certain Grade 3 exceptions discussed below)
- Grade ≥ 4 neutropenia and thrombocytopenia lasting past Cycle 2 Day 28 in the absence of disease (defined as the presence of $<5\%$ bone marrow blasts)

The following Grade 3 events will not be considered DLTs:

- Grade 3 nausea, vomiting, or diarrhea that resolves to Grade 1 or better within 7 days of supportive therapy *and does not require total parenteral nutrition, tube feeding, or prolonged hospitalization*
- Grade 3 asymptomatic or mildly symptomatic rash that can be adequately managed with supportive care (for further details see the Atezolizumab Investigator's Brochure) or resolves to become asymptomatic and/or Grade ≤ 2 within 7 days of supportive therapy
- Grade 3 fatigue, *asthenia, or fever* that resolves to Grade ≤ 2 within 7 days
- Grade 3 arthralgia that can be adequately managed with supportive therapy or that resolves to Grade ≤ 2 within 7 days
- *Asymptomatic Grade 3 laboratory abnormalities (other than liver enzyme and creatinine elevations) that resolve to Grade <2 within 72 hours*

All DLTs will be reported on an electronic Case Report Form (eCRF), the standard Adverse Event eCRF in the Sponsor's electronic data capture (EDC) system within 24 hours (see Section 5.3.5). All DLTs will be considered adverse events of special interest for this protocol and will be reported to the Sponsor in an expedited manner, as indicated in Section 5.2.3. Dose modification decisions will be made by the Sponsor in consultation with investigators after review of available relevant data.

3.1.2.4 *Stopping Rule for Excess Toxicity for Expansion Phase*

Early stopping boundaries for the expansion cohort are based on the Pearson-Klopper confidence intervals of the observed toxicity rate, and a target toxicity rate of no more than 20%. The stopping boundary for a given number of enrolled patients is the minimum number of patients with excess toxicity that would lead to a toxicity rate with its lower 95% confidence boundary higher than 20% (see Table 1. During the expansion phase, an episode of excess toxicity will be defined as any adverse event meeting criteria for a DLT as outlined in Section 3.1.2.3.

Table 1 Early Stopping Boundaries for Expansion Cohort

Number of Patients Enrolled	Stopping Boundary (Number of Patients Who Experience Excess Toxicity)	Observed Toxicity Rate ^a	95% Confidence Interval
3	3	100%	(29%, 100%)
4	4	100%	(40%, 100%)
5	4	80%	(28%, 99%)
6	4	78%	(22%, 96%)
7	5	71%	(29%, 96%)
8	5	62.5%	(24%, 91%)
9	5	56%	(21%, 86%)
10	6	60%	(26%, 88%)
11	6	55%	(23%, 83%)
12	6	50%	(21%, 79%)
13	7	54%	(25%, 81%)
14	7	50%	(23%, 77%)
15	7	47%	(21%, 73%)

^a The confidence interval for the observed toxicity rate calculated based on the Pearson-Klopper method.

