3.1.2 Safety Evaluation Phase

3.1.2.1 Dose-Limiting Toxicity Assessment

The first 6 patients enrolled in the safety cohort will be eligible for DLT assessment. The DLT assessment window for the safety cohort is 56 days from the first dose of Hu5F9-G4.

All patients who experience a DLT during the DLT assessment window will be considered evaluable for safety evaluation decisions.

Patients who withdraw from study treatment (atezolizumab plus Hu5F9-G4) for any reason other than a DLT during this assessment window will not be considered evaluable for safety evaluation decisions and will be replaced. The total number of enrolled patients in this study will be capped at 21 patients. If patients are replaced prior to DLT assessment, discontinued patients will be counted toward the total limit of 21 patients.

During the DLT evaluation window, patients will not be allowed to make up missed doses; patients will resume dosing at their next scheduled dose. Patients who are unable to receive the next scheduled dose of Hu5F9-G4 or atezolizumab as a result of study treatment-related adverse events will be considered to have met the DLT criteria.

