5.3.1 Adverse Event Reporting Period

Investigators will seek information on adverse events at each patient contact.

All adverse events, whether reported by the patient or noted by study personnel, will be recorded in the patient's medical record and on the Adverse Event eCRF.

After informed consent has been obtained but prior to initiation of study treatment, only serious adverse events caused by a protocol-mandated intervention (e.g., invasive procedures such as biopsies, discontinuation of medications) should be reported (see Section 5.4.2 for instructions for reporting serious adverse events).

After initiation of study treatment, all adverse events will be reported until 30 days after the final dose of study treatment or until initiation of new systemic anti-cancer therapy, whichever occurs first, and serious adverse events and adverse events of special interest will continue to be reported until 135 days after the final dose of study treatment or until initiation of new systemic anti-cancer therapy, whichever occurs first.

Instructions for reporting adverse events that occur after the adverse event reporting period are provided in Section 5.6.

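### The expansion stopping boundary is indexed on enrolled patients, and the plan does not say how to count patients still in Cycles 1-2 or those who leave then without a DLT

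*Combined protocol and SAP*

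**What the plan says.** For expansion, Section 3.1.2.4 defines the limit by enrolment: "The stopping boundary for a given number of enrolled patients is the minimum number of patients with excess toxicity" whose exact 95% lower limit exceeds 20%. The first column of Table 1 is likewise patients enrolled. Excess toxicity is any event meeting the DLT criteria of Section 3.1.2.3, where "Any of the following adverse events that occur during Cycles 1 or 2 will be considered a DLT". Those criteria, if the event is judged related, include "Any adverse event (regardless of NCI CTCAE v5.0 grade) that leads to dose reduction or withdrawal".

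The only evaluability rule is in Section 3.1.2.1, which opens with the first 6 patients of the safety cohort. There, "The DLT assessment window for the safety cohort is 56 days from the first dose of Hu5F9-G4", and "All patients who experience a DLT during the DLT assessment window will be considered evaluable for safety evaluation decisions". A patient who withdraws from treatment "for any reason other than a DLT during this assessment window will not be considered evaluable for safety evaluation decisions and will be replaced". Section 3.1.2.4 refers to the DLT definition but not to this rule. Section 6 defines one analysis population, patients who received any study drug, and no DLT-evaluable set.

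On capture after leaving, Section 3.1.2.3 says that "All DLTs will be considered adverse events of special interest for this protocol". Section 5.3.1 says that "serious adverse events and adverse events of special interest will continue to be reported until 135 days after the final dose of study treatment"; Section 5.6 and Appendix 1 (adverse event footnote) agree. Section 5.4.2.2 gives 30 days for the same events, and Section 5.1 gives 30 days for serious events. Sections 5.3.1 and 5.4.2.2 both end reporting at new systemic anti-cancer therapy.

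**The concern.** The same event is judged on different denominators in the two phases. In the safety cohort, a patient who leaves for a non-DLT reason is removed from the decision. In expansion, such a patient (for example after unrelated death, loss of benefit or withdrawal of consent) stays in the count as a patient without toxicity. A patient still in the window is provisionally counted the same way. Atezolizumab starts on Day 22, so someone who leaves earlier was never at risk of a combination DLT but still lowers the observed rate.

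Table 1 is the only numerical toxicity limit in expansion. Enrolment could therefore continue after the patients who can inform the decision have crossed the 20% criterion. Reporting of DLTs within 24 hours and the sponsor's right to terminate the study remain, but neither sets a number.

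**Working it through.** **Inputs.** 20% target, exact interval, n = 3 to 15 (Section 3.1.2.4, Table 1); 56-day window (3.1.2.1, and Cycles 1-2 of 28 days); 21 patients in 22 months, about 1 per month (3.2); dosing days (3.1.1). Dropout is assumed, because the documents give no rate.

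**1. Reproduce Table 1.** For each n, take the smallest r for which the two-sided 95% Clopper-Pearson lower limit, the 2.5% quantile of Beta(r, n - r + 1), exceeds 20%. This gives 3, 4, 4, 4, 5, 5, 5, 6, 6, 6, 7, 7, 7 for n = 3 to 15: all 13 boundaries. A one-sided limit does not reproduce them (it gives 3 at n = 4).

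**2. Shift caused by leavers.** With k leavers and no DLT registered for them, the extra DLTs needed are boundary(n) - boundary(n - k).

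- k = 1: one more at n = 4, 7, 10 and 13, that is 4 of 12 counts.
- k = 2: one more at n = 5, 7, 8, 10, 11, 13 and 14, that is 7 of 11.
- k = 3: one more at every n from 6 to 15, that is 10 of 10.

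Example: 10 enrolled, 1 leaver, 5 DLTs. The lower limit for 5/9 is 21.2%, and 5 is the boundary at 9. The lower limit for 5/10 is 18.7%; the boundary is 6, so enrolment continues.

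**3. Days covered after leaving, 30-day reading.** Last dose on Day 8: 8 + 30 = Day 38. Day 22: 22 + 30 = Day 52. Day 29: 29 + 30 = Day 59. A patient last dosed on or before Day 22 is therefore not covered to Day 56. On the 135-day reading every leaver is covered, unless new anti-cancer therapy starts.

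**4. Stopping probability of the enrolled rule, 15 patients, true DLT rate 40%.** Simulation: exponential arrivals at 1 per month; DLT and leaving times uniform over 56 days; each DLT counted when it occurs against the number then enrolled.

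| Assumed non-DLT dropout | No capture after leaving | 30-day capture | Full capture |
|---|---|---|---|
| 0% | 44% | 44% | 44% |
| 10% | 38% | 43% | 44% |
| 20% | 33% | 41% | 44% |
| 30% | 27% | 39% | 44% |

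With 30-day capture about 74% of DLTs after leaving are registered. This ignores new anti-cancer therapy and withdrawal of consent, which would lower it. If every outcome were known at once, the exact stopping probability would be 47%, so pending patients alone cost about 3 points.

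**5. Cost of an evaluable-only boundary.** Let p be the true rate, d the dropout and q the share of later DLTs registered. Then P(evaluable with DLT) = p[1 - (d/2)(1 - q)] and P(evaluable without DLT) = (1 - p)(1 - d). At p = 20%, the probability of crossing at some point is:

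| d | Evaluable, q = 0 | Evaluable, q = 1 | Enrolled, no capture | Enrolled, full capture |
|---|---|---|---|---|
| 10% | 4.7% | 5.6% | 2.8% | 3.4% |
| 20% | 5.3% | 7.2% | 2.1% | 3.4% |
| 30% | 5.9% | 9.5% | 1.7% | 3.4% |

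The rise comes from selection on outcome: a DLT keeps a patient in the set, and leaving without one removes the patient. At a true 40% with q = 0, the apparent rate is 41.3%, 42.9% and 44.7% at 10%, 20% and 30% dropout.

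**The case against.** An all-enrolled denominator is a legitimate choice. It matches the analysis population in Section 6, and the two phases need not share a denominator: the first 6 patients drive a dose decision with replacement, while expansion has a monitoring limit. Patients withdrawn for a related adverse event already count as DLTs. The window is largely imported through the DLT definition, and the withdrawal sentence in 3.1.2.1 could be stretched to expansion because both sections sit under 3.1.2. One leaver changes nothing at 8 of 12 counts.

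Much of this stands. It shows that Table 1 is not miscalculated and should not be replaced. It does not supply the missing rule: stretching 3.1.2.1 is arguable, but the text does not say it.

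The strongest objection concerns size. A reader might infer from the no-capture column that the rule loses 11 points at 20% dropout (44% to 33%). The documents do not support that as the expected loss. DLTs are events of special interest, even the shorter reading reports them for 30 days, a discontinuation visit falls within 30 days of the final dose, and Section 5.6 asks for later related serious events that the investigator learns of. With 30-day capture the loss is 3 points; with full capture there is none.

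**Conclusion.** The gap is real and modest. Expansion has no stated rule for leavers without a DLT or for patients still in the window, and the literal count treats both as non-toxic. At 10%, 20% and 30% assumed dropout and a true rate of 40%, the loss in stopping probability is about 1, 3 and 5 points with 30-day capture, 6, 11 and 17 with none, and zero with full capture. For pending patients the effect is mainly delay; for leavers whose later DLTs are missed it is permanent.

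The result rests on assumed dropout, uniform event times and steady accrual. The early-death figures in Section 1.2.4 concern front-line MDS and are not a dropout rate for this trial.

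A reader might also infer that an evaluable-only boundary should replace Table 1 as an automatic stop. The documents do not require this, and the figures argue against it: at a true rate equal to the 20% target it would cross in about 5% to 9% of trials, against about 2% to 3% for the present rule at 10% to 30% dropout.

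**What to change.** 1. Reconcile the reporting periods in 5.1, 5.3.1, 5.4.2.2, 5.6 and Appendix 1. State that DLTs in patients who leave treatment are captured to Day 56 where consent allows.
2. State in 3.1.2.4 that the Cycles 1-2 window applies to expansion.
3. Keep Table 1 on enrolled patients as the immediate rule, counting each DLT when it is reported. Beside it, apply the same 13 boundaries to DLT-evaluable patients: those with a DLT in the window, or who completed the window on treatment without one. If only this second count crosses, the sponsor carries out a documented review of the excluded and pending patients before further enrolment. It is not an automatic stop.

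The cost is a few sentences and a second count over at most 15 patients. The downside is that the second count selects on outcome and so crosses too often at the target rate, which is why it should trigger review only. The 20% target and all boundaries stay.

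Two separate points. Section 4.6.1 says patients who discontinue treatment are not replaced and 4.6.2 says those who withdraw from the study are; reconcile both with the cap of 21, which 6 + 15 or 12 + 9 already fills. In the n = 6 row of Table 1 the observed rate should read 67% (4/6), not 78%; this is clerical and changes no boundary or interval.

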3.2 END OF STUDY AND LENGTH OF STUDY

The end of this study is defined as the date when the last patient, last visit (LPLV) occurs. The last patient is expected to be enrolled 22 months after the first patient is enrolled, and the LPLV is expected to occur approximately 15 months after the last patient is enrolled. The total study duration is therefore expected to take approximately 37 months.

3.3 RATIONALE FOR STUDY DESIGN

3.3.1 Rationale for Atezolizumab Dose and Schedule

Atezolizumab will be administered at a fixed dose of 840 mg IV Q2W (840 mg on Days 8 and 22 of each 28-day cycle). The exception will occur at Cycle 1, when only 1 cycle dose of atezolizumab will be administered at a fixed dose of 840 mg IV on Day 22 (biomarker-driven treatment schedule). The starting dose and schedule of atezolizumab 840 mg IV Q2W is currently approved in the United States in several indications, including urothelial carcinoma, non-small cell lung cancer, triple-negative breast cancer, and small cell lung cancer (Tecentriq® U.S. Package Insert). Based on the mechanism of action of the drug, pathophysiology of disease, and study population characteristics, it is not expected that the safety profile would be different for the AML population. Thus, atezolizumab 840 mg Q2W could be considered a safe starting dose and schedule. The dosing schedule used in this protocol is similar to the atezolizumab

dosing schedule tested in previous clinical studies in patients with myeloid malignancies, such as relapsed/refractory and previously untreated AML and relapsed/refractory and previously untreated myelodysplastic syndrome (ClinicalTrials.gov Identifier: NCT02935361 and NCT02508870).

3.3.2 Rationale for Patient Population

Although the single-agent clinical activity of both atezolizumab and Hu5F9-G4 is limited in patients with advanced myeloid malignancies (*ORR of ≤ 10%*), preclinical exposure to Hu5F9-G4 is known to elicit a robust anti-tumor T-cell response. As such, in a sarcoma model, the combination of anti-CD47 (pro-phagocytic) and anti-cytotoxic T lymphocyte-associated protein 4 (anti-CTLA-4) (increased T-cell activation) antibodies results in decreased tumor growth and tumor regression compared with each used alone (refer to the Hu5F9-G4 Investigator's Brochure). In addition, PD assessment of bone marrow biopsies from patients with AML treated with Hu5F9-G4 demonstrated a significant increase in the bone marrow infiltrate of T cells, suggesting that sequential inhibition of CD47 signaling followed by blockade of PD-L1 may lead to clinical activity in patients with advanced myeloid malignancies.

The median T-cell population in bone marrow aspirates of patients with AML is 8%–25% (Daver et al. 2016). T cells make up a significantly larger proportion of the CD45-positive population (non-leukemic cells) in bone marrow aspirates from patients with AML compared with healthy donors (Daver et al. 2018). T cells in patients with AML exhibit distinct phenotypic and genotypic differences from T cells of healthy donors. The T cells in the bone marrow of patients with AML express activation markers (such as CD25, CD69, OX40) at a significantly higher rate than seen in healthy donors, indicating that the AML bone marrow is an inflamed microenvironment (Vidriales et al. 1993; Van den Hove et al. 1998). There is an increased overall expression of inhibitory surface molecules associated with T-cell exhaustion of CD4+ and CD8+ T cells in patients with AML compared with controls (Snorfeil et al. 2013; Daver et al. 2016; Tan et al. 2016). In addition, compared with healthy controls, patients with relapsed and newly diagnosed AML had a higher percentage of exhausted T-cell phenotype (PD-1+ TIM3+ and PD-1+ LAG3+ CD8 T cells) in the bone marrow (Williams et al. 2017). PD-1 expression on the T cells in bone marrow was higher in multiple-relapsed AML compared with first-salvage AML, newly diagnosed AML, or healthy donors (PD-1 on T cells in patients with multiple relapsed AML, which were greater than in patients receiving first salvage therapy and greater than in newly diagnosed patients, which were greater than in healthy donors), suggesting progressive T-cell exhaustion with more advanced-stage AML (Daver et al. 2016).

There are no approved treatments for patients with AML who are unable to achieve an initial CR or patients who relapse after initial response, with poor survival among this group of patients. Therefore, there is a high unmet medical need for new therapies for patients with R/R AML.

On the basis of these data, there is a strong preclinical and PD rationale for exploring the use of atezolizumab in combination with Hu5F9-G4 in patients with R/R AML. Finally, it is unclear why the PD-L1-positive immune-cell infiltrate present in the bone marrow of patients with AML and MDS is unresponsive to checkpoint modulation. Therefore, an unselected patient population will be enrolled in order to obtain samples for exploratory biomarkers of checkpoint resistance.

[figure not shown]
3.3.3 **Rationale for Relapsed and/or Refractory AML**

Between 10% and 40% of newly diagnosed patients with AML do not achieve CR with intensive induction therapy and are therefore categorized as having disease that is primary refractory or resistant. In addition, between 30% and 80% of patients who achieve a CR will subsequently relapse. Few of these patients can be cured with conventional salvage therapy (Thol et al. 2015). Most patients with R/R AML should be enrolled in clinical trials, given that highly effective and standardized treatments for AML are lacking and clinical trial enrollment is encouraged in this population.

3.3.4 **Rationale for Hu5F9-G4 Dose**

The dosing schedule chosen for Hu5F9-G4 was established during the Phase I clinical trial, during which no MTD was identified at doses of up to 30 mg/kg twice a week. In addition, PD assessments, conducted during the same Phase I clinical trial demonstrated that a priming dose for the first week, followed by escalating doses during the second week, and subsequently by weekly doses of the anti-CD47 monoclonal antibody, was not associated with early deaths, was safe and well tolerated in AML patients, resulted in a linear PK profile (see [Figure 2](#)), and optimal CD47 antigen binding in bone marrow at steady state (see [Figure 2](#)).

Figure 2 Hu5F9-G4 Achieves Target PK Levels at Clinically Feasible Doses

- 5F9 can overcome the CD47 antigen sink at 10 mg/kg or higher
- Antibody half-life is ~13 days
- Free plasma drug levels exceed preclinical activity thresholds identified from PK modeling (>100 to 250 μg/ml)

5F9 = Hu5F9-G4; PK = pharmacokinetic.

Source: Agoram et al. 2018.

